9.6 Change in Categorical PaO₂/FiO₂ Ratio (Mild, Moderate, and Severe)

PaO₂/FiO₂ ratio will be defined as a categorical variable using Berlin criteria for ARDS categorization (mild, moderate, severe), where mild is PaO₂/FiO₂ from >200 to <=300, moderate is from 100 to <=200, and severe is <100. Proportion of subjects of each category at baseline and Day 28 will be summarized descriptively.

9.7 Change from Baseline in PaO₂/FiO₂ Ratio and Change from baseline in Resting SpO₂/FiO₂ at Day 28

Change from baseline in PaO₂/FiO₂ ratio at Day 28 and change from baseline in resting SpO₂ adjusted by FiO₂ (SpO₂/FiO₂) at Day 28 will be summarized descriptively.

9.8 Change in (Non-invasive) Oxygen Supplementation Requirements at Day 28

The non-invasive oxygen supplementation requirements include:

- (1) No oxygen supplementation (including breathe room air or have been discharged from hospital)
- (2) Non-invasive oxygen supplementation -nasal cannula and face-mask

Change in non-invasive oxygen supplementation requirements will be presented by proportion of subjects with non-invasive oxygen supplementation requirements at baseline and at Day 28.

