4.2 Secondary Efficacy Endpoints

- Proportion of subjects alive, discharged home, and not on supplemental oxygen at Day 28
- Proportion of subjects who never received mechanical ventilation and/ or ECMO and alive at Day 14
- Time to recovery by Day 28 based on the NIAID 8-point ordinal scale (Day of recovery is defined as the first day on which the patient satisfies one of the following three

categories from the ordinal scale: (1) Not hospitalized, no limitations on activities; (2) Not hospitalized, limitations on activities and/or requiring home oxygen; (3) Hospitalized, not requiring supplemental oxygen, no longer requiring medical care (used if hospitalization was extended for infection-control reasons)

- Clinical status based on the NIAID 8-point ordinal scale (time range: Days 1 to 28)
- Days in ICU/CCU (either on or off mechanical ventilation and/or ECMO) at Day 28
- Days on mechanical ventilation and/or ECMO at Day 28
- Time to mechanical ventilation/ECMO or all-cause mortality at Day 28
- All-cause mortality at Day 28 (proportion of subjects deceased)
- Time to death from any cause at Day 28
- Change in $\text{PaO}_2/\text{FiO}_2$ ratio as categorical variable using Berlin criteria for ARDS categorization (mild, moderate, severe) (time range: Days 1 to 28)
- Change in $\text{PaO}_2/\text{FiO}_2$ ratio as continuous variable (time range: Days 1 to 28)
- Change in resting SpO_2 adjusted by FiO_2 (time range: Days 1 to 28)
- Change in (non-invasive) oxygen supplementation requirements (time range: Days 1 to 28)

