Proportion of subjects by response category on the NIAID 8-point ordinal scale will be summarized descriptively based on observed data at baseline and Day 28.

Order	Ordinal Level
1	Not hospitalized, no limitations on activities
2	Not hospitalized, limitations on activities and/or requiring home oxygen
3	Hospitalized, not requiring supplemental oxygen, no longer requiring medical care (used if hospitalization was extended for infection-control reasons)
4	Hospitalized, not requiring supplemental oxygen, requiring ongoing medical care (COVID-19-related or otherwise)
5	Hospitalized, requiring supplemental oxygen
6	Hospitalized, requiring high-flow oxygen, non-invasive mechanical ventilation, or both

7	Hospitalized, requiring invasive mechanical ventilation, extra-corporeal membrane oxygenation (ECMO), or both
8	Death
Missing	

9.5 Number of Days in ICU/CCU and Number of Days on Mechanical Ventilation and/or ECMO

Total number of days in ICU/CCU (either on or off mechanical ventilation and/or ECMO) at Day 28 and total number of days on mechanical ventilation and/or ECMO at Day 28 will be summarized descriptively.

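### SAP 9.6 and 9.8 report two change endpoints only as separate baseline and Day 28 proportions, which cannot show how many subjects changed

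*SAP*

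**What the plan says.** SAP 4.2 lists change in PaO₂/FiO₂ as a categorical variable among the secondary endpoints. It words the oxygen endpoint as "Change in (non-invasive) oxygen supplementation requirements (time range: Days 1 to 28", closing the bracket there. The headings of SAP 9.6 and 9.8 both name a change.

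The analyses are as follows.

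- **SAP 9.6 (categorical PaO₂/FiO₂):** "Proportion of subjects of each category at baseline and Day 28 will be summarized descriptively". The only levels are mild (above 200 up to 300), then "moderate is from 100 to <=200, and severe is <100".
- **SAP 9.8 (oxygen requirement):** the change "will be presented by proportion of subjects with non-invasive oxygen supplementation requirements at baseline and at Day 28". There are two levels. The first is "No oxygen supplementation (including breathe room air or have been discharged from hospital"); the second is nasal cannula and face mask.
- **SAP 9 (opening paragraph):** efficacy is summarized on observed data for the ITT population, and missing endpoint values are not imputed.
- **SAP 5.1:** no treatment comparison will be made.

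Neither 9.6 nor 9.8 states a denominator, a cross-tabulation or a count of subjects improved, unchanged or worsened. SAP 9.7, by contrast, summarizes change from baseline for the continuous PaO₂/FiO₂ and SpO₂/FiO₂ ratios.

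**The concern.** A change endpoint is about what happened to each subject between two times. Two separate distributions describe the group at each time and discard the pairing, so the table headed as change does not contain it. This is so even with complete data.

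Missing data add a second problem. PaO₂/FiO₂ needs an ABG. Under Protocol Amendment 1 (Section 6.1 and the Schedule of Assessments footnote), ABGs are required daily only in ICU/CCU, are otherwise recorded only if done as routine care, and stop at discharge. Subjects who go home or die will therefore generally have no Day 28 value. If the sickest or the healthiest leave the observed set, the Day 28 column shifts although no remaining subject has moved. Descriptive tables are the only efficacy output this trial will have, so a reader has little else to correct that impression.

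**Working it through.** The plan gives no figure for these two tables, so there is none to reproduce. The power statement in Protocol 9.1 concerns the primary endpoint and is not used here.

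**Inputs**

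- 22 subjects randomized (SAP 1), allocated 1:1 (SAP 3). The per-arm count is not stated; 11 per arm is assumed.
- All category counts below are assumed, for illustration only.

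**1. Margins do not identify change, even with nobody missing**

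Let n be the subjects seen at both times, b the number in a category at baseline, f the number in it at Day 28, and x the number in it at both. Then x lies between max(0, b + f − n) and min(b, f). The number leaving is b − x, the number entering is f − x, and the number changing is b + f − 2x.

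- b = 5, f = 5, n = 11: x runs from max(0, −1) = 0 to 5. The number changing runs from 10 − 2×5 = 0 to 10 − 2×0 = 10. The planned table prints 45.5% and 45.5% in every case.
- The upper limit does not depend on exactly 11 per arm: for any n of 10 or more, b + f − n is at most 0 and the range stays 0 to 10. For n = 9, x is at least 1 and the range is 0 to 8.
- On oxygen 8/11 at baseline and 5/11 at Day 28 (9.8): x runs from max(0, 2) = 2 to 5. Improved (leaving) is 3 to 6 and worsened (entering) is 0 to 3.

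**2. Attrition alone in 9.6**

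Baseline mild/moderate/severe is 4/4/3 of 11, that is 36.4%, 36.4% and 27.3%. No subject still observed changes category.

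| What happens by Day 28 | Observed mild/moderate/severe | Percentages | Reads as |
|---|---|---|---|
| 3 severe die, 2 moderate discharged without ABG | 4/2/0 of 6 | 66.7 / 33.3 / 0 | improvement |
| 4 mild discharged without ABG | 0/4/3 of 7 | 0 / 57.1 / 42.9 | worsening |

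The first row turns three deaths into the disappearance of severe disease. The second turns four discharges into a shift towards severe disease.

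**3. Attrition alone in 9.8**

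Discharged subjects have a level here, so the loss comes from death, invasive ventilation/ECMO and missing data. Take 8/11 (72.7%) on oxygen at baseline. Four of them die or are ventilated, and the other seven subjects do not change. At Day 28, 4 remain on non-invasive oxygen: 4/7 = 57.1% of those with a defined level, or 4/11 = 36.4% on a fixed denominator. Either figure reads as a reduced need for oxygen.

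**The case against.** The case for leaving the SAP alone has real substance.

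- **Within-subject change is computed elsewhere.** SAP 9.7 takes change from baseline in the same PaO₂/FiO₂ ratio that 9.6 cuts into bands, and SAP 5 puts all collected data in listings. With 22 subjects the transitions can be recovered by hand, and deaths are summarized in 9.2 and listed under 10.1. A reader might infer that the SAP never computes any subject's change. That is not so: the gap is in the categorical summaries only.
- **SAP 9.4 looks similar but is different.** A reader might extend the point to it, since the ordinal scale is also summarized "will be summarized descriptively based on observed data at baseline and Day 28". But SAP 4.2 names that endpoint as clinical status, not change, and its table has Death and Missing rows. It needs no correction.
- **Proportions have a precedent in the protocol.** Protocol 9.4 planned to analyze the categorical PaO₂/FiO₂ endpoint through proportions, so to say that the endpoint is not estimated at all would go too far for 9.6. This defence does not cover 9.8, because the protocol planned a repeated-measures model of change in oxygen requirement.
- **Different subjects in the two columns is a risk, not a stated fact.** The denominators are not given, and 9.8 keeps discharged subjects in the table.
- **Nothing inferential depends on these tables.**

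All of this limits scope and weight. It does not answer the core point: a summary presented as change should show change, and a listing does not repair a table that can print deaths as improvement.

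**Conclusion.** The point holds for SAP 9.6 and 9.8. As specified, neither table can show how many subjects improved, worsened or stayed the same, and both can show movement produced only by subjects leaving the defined levels. The non-identification follows from the layout alone. The 0 to 10 range rests on the assumed 11 per arm and 5/11 at both times. The attrition examples rest on assumed counts; they show what the rule permits, not what occurred in this trial.

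Severity is minor. These are secondary, descriptive tables for 22 subjects with no treatment comparison, and the primary endpoint is untouched. A reader might infer that the trial's efficacy conclusion is compromised; the documents do not support that, because SAP 5.1 rules out any comparison between arms.

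**What to change.** In SAP 9.6 and 9.8, replace the two marginal columns with a by-arm shift table of baseline level against Day 28 level, covering all randomized subjects.

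- **9.6:** add a level for PaO₂/FiO₂ above 300, a row for no baseline ABG, and Day 28 columns for death, discharged without ABG, and other missing. Without the first two additions, a recovered inpatient or a subject outside ICU/CCU at baseline may have no cell.
- **9.8:** add levels for invasive ventilation/ECMO, death and missing.
- **Both:** report the number improved, unchanged and worsened among subjects classifiable at both times, and count the unclassifiable separately. State beforehand which transitions count as improved or worsened.

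Leave 9.4 and 9.7 as they are. The cost is a few lines of SAP text and two small tables from data already collected, with no imputation. The downside is sparse cells at about 11 subjects per arm, which is acceptable because counts, not percentages, carry the message.

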³ Need for mechanical ventilation/ECMO, including ventilator settings, or supplemental oxygen, including mode of oxygen delivery. ⁴ Collected until Day 28 or hospital discharge, whichever occurs earlier 5 ABGs are collected daily while in ICU/CCU, and recorded if performed as part of routine care outside of ICU/CCU, until Day 28 or hospital discharge, whichever occurs earlier ⁶ if subject is discharged, these visit do not apply; subject should return for infusion visits only. ⁷ If a subject is discharged from hospital before Day 28, and unwilling to return for visits and infusions in an outpatient setting, visits may be conducted remotely for assessment of vital status and safety. If a subject is lost to follow-up after hospital discharge, vital status may also be obtained from public records. 8 Visit windows, for outpatient dosing visits ONLY: visit window for Day 14: +/- 2 days. Visit window for Day 28: +/- 3 days.

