9 EFFICACY ANALYSES

Efficacy data will be summarized descriptively based on observed data for the ITT population. There will be no imputation performed for the missing endpoint value.

9.1 Primary Efficacy Endpoint - Proportion of Subjects who Never Received Mechanical Ventilation and/or ECMO and Alive at Day 28

Proportion of subjects never received mechanical ventilation and/or ECMO and alive at Day 28 will be summarized based on observed data.

9.2 Proportion of Subjects Alive, Discharged, and not on Supplemental Oxygen, Proportion of Subjects who Never Received Mechanical Ventilation and/ or ECMO and Alive, and Proportion of Subjects Deceased

Proportion of subjects alive, discharged home, and not on supplemental oxygen at Day 28, proportion of subjects never received mechanical ventilation and/ or ECMO and alive at Day 14, and proportion of all-cause deaths at Day 28 will be summarized descriptively based on observed data.

9.3 Time to Recovery, Time to Mechanical Ventilation/ECMO or All-cause Mortality, and Time to death

- Time (number of days) from randomization to recovery by Day 28 based on NIAID 8-point ordinal scale where recovery is defined as the first day on which the patient satisfies one of the following three categories from the ordinal scale: (1) Not hospitalized, no limitations on activities; (2) Not hospitalized, limitations on activities and/or requiring home oxygen; (3) Hospitalized, not requiring supplemental oxygen, no longer requiring medical care (used if hospitalization was extended for infection-control reasons)

Subjects without the event will be censored at the date of last NIAID 8-point ordinal scale assessment.

- Time (number of days) from randomization to mechanical ventilation/ECMO or all-cause mortality by Day 28

For subjects who did not have the event, the last known assessment date of mechanical ventilation/ECMO use or survival status, whichever later will be defined as the censoring date.

- Time (number of days) from randomization to death from any cause by Day 28

For subjects who are alive, the recorded date of last known alive, last contact date, or the date of the last clinic visit, whichever latest will be defined as the censoring date.

The number of days of the above endpoints will be summarized descriptively as appropriate.

9.4 Clinical Status Based on the NIAID 8-point Ordinal Scale at Day 28

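### SAP 9.8 has no level for invasive ventilation, ECMO or death and states no denominator, so the oxygen-requirement row read alone can show deterioration as reduced need

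*SAP*

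**What the plan says.** Change in non-invasive oxygen supplementation is the last of the 13 secondary endpoints in SAP 4.2. SAP 9.8 defines two states. One is "1) No oxygen supplementation (including breathe room air or have been discharged from hospital"; the other is "Non-invasive oxygen supplementation -nasal cannula and face-mask". Change is then "presented by proportion of subjects with non-invasive oxygen supplementation requirements at baseline and at Day 28". Nothing in 9.8 says which subjects form the denominator, or what happens to a subject in neither state.

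The general rules at the head of SAP 9 do not fill the gap: "Efficacy data will be summarized descriptively based on observed data for the ITT population", and "There will be no imputation performed for the missing endpoint value".

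The SAP draws finer distinctions elsewhere. The ordinal scale in SAP 9.4 separates supplemental oxygen (level 5), high-flow oxygen or non-invasive ventilation (level 6), "Hospitalized, requiring invasive mechanical ventilation, extra-corporeal membrane oxygenation (ECMO), or both" (level 7) and death (level 8), with a row for missing values. It is tabulated at the same two time points, baseline and Day 28.

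The data for finer levels are scheduled. Footnote 3 to the schedule in Protocol Amendment 1, Appendix 1, specifies collection of "Need for mechanical ventilation/ECMO, including ventilator settings, or supplemental oxygen, including mode of oxygen delivery". The same schedule includes the ordinal scale and survival status. Footnote 4 stops collection of oxygen needs at hospital discharge if that comes before Day 28.

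**The concern.** Eligibility (Protocol Amendment 1, Section 5.1) excludes subjects on mechanical ventilation or ECMO at randomization, so entry to those states, and death, happens only after baseline. A subject who starts on cannula or mask and is intubated or dead at Day 28 is in neither state of SAP 9.8. That subject leaves the count of those needing non-invasive oxygen, and so does a subject who recovers to room air. The row does not say which happened.

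At stake is whether one named secondary endpoint can be read correctly from its own table. A fall in the proportion looks like benefit, but part of it may be patients getting worse. With about 11 subjects per arm if the 1:1 allocation held, one such subject moves the figure noticeably.

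**Working it through.** SAP 9.8 gives no figure to reproduce, so the check has two parts: where each outcome lands under the wording, and what that does to the proportion.

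**Where a subject on cannula or mask at baseline lands at Day 28**

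| Status at Day 28 | Level in SAP 9.4 | State in SAP 9.8 | Effect on the oxygen count |
|---|---|---|---|
| Room air in hospital | 3 or 4 | none | leaves |
| Discharged | 1 or 2 | none | leaves |
| Still on cannula or mask | 5 | cannula or mask | stays |
| High-flow or non-invasive ventilation | 6 | not named | stays or leaves, depending on coding |
| Invasive ventilation or ECMO | 7 | no state | leaves |
| Dead | 8 | no state | leaves |

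**Illustration**

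Inputs: 22 subjects randomized (SAP 1) and 1:1 allocation (SAP 3) give about n = 11 per arm; the actual split is not stated. The remaining inputs are assumptions: k subjects on cannula or mask at baseline, nobody improves, and w of the k are ventilated, on ECMO or dead at Day 28. Because no denominator is stated, two are shown.

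- All subjects: (k − w)/n. The fall from baseline is w/n, so each worsened subject takes off 1/11 = 9.1 points.
- Only the two listed states: (k − w)/(n − w). The fall is k/n − (k − w)/(n − w) = w(n − k)/[n(n − w)], which is zero when k = n.

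| k | w | Baseline | Day 28, all subjects | Day 28, two states only |
|---|---|---|---|---|
| 9 | 1 | 9/11 = 81.8% | 8/11 = 72.7% | 8/10 = 80.0% |
| 9 | 2 | 9/11 = 81.8% | 7/11 = 63.6% | 7/9 = 77.8% |
| 9 | 4 | 9/11 = 81.8% | 5/11 = 45.5% | 5/7 = 71.4% |
| 7 | 2 | 7/11 = 63.6% | 5/11 = 45.5% | 5/9 = 55.6% |
| 11 | 2 | 11/11 = 100% | 9/11 = 81.8% | 9/9 = 100% |

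For comparison, if k = 9 and two subjects recover to room air while nobody worsens, the Day 28 figure is 7/11 = 63.6%. With all subjects as denominator, two recoveries and two deaths give the same number.

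**If both states are printed as rows** (k = 9, w = 2)

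- All subjects as denominator: no oxygen stays at 2/11 = 18.2% and cannula or mask is 63.6%. The rows sum to 9/11 = 81.8%, against 100% at baseline. The missing 18.2% is visible but unlabelled.
- Two states as denominator: no oxygen rises to 2/9 = 22.2% and cannula or mask falls to 77.8%. The rows sum to 100%, and nothing shows that two subjects worsened.

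**The case against.** The strongest reply is that 9.8 lists both states under the heading of oxygen requirements, so the table may print both rows. With the whole ITT population as denominator, recovery raises the first row, while intubation or death raises neither. This stands in part: the two can then be told apart by inference. It depends on a denominator the SAP does not state, and the shortfall would mix ventilated, dead and missing subjects.

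The second reply is scope. The endpoint is labelled non-invasive, and ventilation and death are reported in SAP 9.1 to 9.5. The table in 9.4 already shows levels 5 to 8 at the same time points. This largely stands and is the main reason the point is minor. It does not make the 9.8 row safe to read alone, and a pair of marginal tables does not show who moved where.

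Three stronger readings are tempting, and the documents do not support them.

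- *High-flow subjects certainly leave the count.* SAP 9.8 does not name high-flow oxygen. It could be coded as cannula, and mask-delivered non-invasive ventilation as mask; that worsening would then show as no change.
- *Worsening can only move subjects out of the cannula-or-mask state.* Section 5.1 also admits subjects on imaging findings or on low room-air saturation. They can start on no oxygen and worsen into that state, which raises the proportion in the right direction.
- *The worse arm will look better.* Apply the planning failure rates of 35% and 15% (from the 65% and 85% in Protocol Amendment 1, Section 9.1). Suppose everyone starts on cannula or mask, failures are still ventilated or dead at Day 28, and one third of event-free subjects still need oxygen. The Day 28 figures are then 0.65/3 = 21.7% on placebo and 0.85/3 = 28.3% on pamrevlumab. The one-third has no source in the documents, eligibility does not require oxygen at baseline, and the failure rates were planned for about 130 subjects. With only the two states as denominator, both arms show 33.3%, so there is no reversal.

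**Conclusion.** The gap is real for invasive ventilation, ECMO and death: followed as written, SAP 9.8 removes these subjects from the oxygen count as it removes recovered ones, and no other rule in SAP 9 restores them. For high-flow oxygen and non-invasive ventilation the finding is only that the coding is ambiguous.

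The size cannot be predicted from the documents. In the illustrative arm of 11 with 9 on oxygen and 2 worsening, the apparent reduction in need is 18.2 points with all subjects as denominator (81.8% − 63.6%) and 4.0 points with the two states only (81.8% − 77.8%). It is zero under the second denominator if everyone starts on oxygen. These figures rest on the assumed k and w, an even split, and nobody improving.

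Severity is minor. The endpoint is one of 13 secondary endpoints, SAP 5.1 rules out treatment comparisons, and ventilation and death appear elsewhere in the report. It is worth correcting because the correction is cheap and needs no new data collection.

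**What to change.** In SAP 9.8, replace the two states with mutually exclusive levels:

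- in hospital, no oxygen
- nasal cannula or face-mask
- high-flow oxygen or non-invasive ventilation
- invasive ventilation or ECMO
- dead
- discharged, split by ordinal level 1 versus level 2 where recorded
- unknown

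Use all randomized subjects in the arm as the denominator at both time points, and show the baseline-to-Day-28 shift by arm.

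The discharged level needs a footnote. Oxygen needs are not collected after discharge, and ordinal level 2 combines activity limitation with home oxygen, so it cannot be read as home oxygen alone. Subjects followed remotely may have no ordinal level at Day 28; those known to be discharged should be shown as discharged with level not recorded, so that they are not assumed to need no oxygen.

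The cost is a revised paragraph and one table shell, since delivery mode, ventilation or ECMO, ordinal level and survival status are all on the schedule. The downside is sparse cells with 22 subjects; counts should be shown beside every percentage.
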